13.0 Risks to Subjects

13.1 The risks to the subjects in the trial are the same risks found in standard clinical practice and patients wearing contact lenses outside of a controlled trial. During study procedures, there is the risk of mild discomfort due to light being shined on the eye, through the use of topical ophthalmic diagnostic agents, or insertion of contact lenses. The usual risks which exist during the performance of tear collection may include minor eye discomfort, irritation, and temporary redness of the eyes. The discomfort is usually self-limiting and can be resolved with the use of over the counter artificial tears. A break will be given if the subjects experience any discomfort or irritation during tear collection.

Contact lenses will be fit as part of this study. The US Food and Drug Administration consider daily wear contact lenses Class II medical devices. While most individuals wear

FULL PROTOCOL TITLE: Toric Contact Lens Digital Performance and Comfort Study

contact lenses without problems, there are some risks associated with wearing contact lenses. Ulcerative keratitis (infection of the clear front part of the eye), is the most severe risk and can lead to loss of vision. Ulcerative keratitis is estimated to happen to about 1-2 out of 10,000 people who use daily wear, daily disposable contact lenses. The risk for ulcerative keratitis in this study is no different than the risk found with contact lens fitting in standard clinical practice. The risk of ulcerative keratitis may be reduced by educating subjects to carefully following the study doctor's directions for lens care, including throwing out contact lenses each night, never sleeping or napping in contact lenses, and never exposing the contact lenses to water. These study instructions are the same as those provided to subjects in clinical practice

In addition to ulcerative keratitis, the following problems may occur when wearing contact lenses:

- Other, less serious, infections or inflammation of the eye(s)
- Burning, stinging, itching, dryness or general irritation of the eye(s)
- Corneal neovascularization (small blood vessels growing into the cornea)
- Excessive watering, unusual eye secretions, or redness of the eye
- Reduced or blurred vision (compared to glasses)
- Seeing rainbows or halos around bright lights (compared to glasses)

Many of the potential problems associated with contact lens wear are self-limiting and can be resolved with discontinuation of lens wear. These problems can be minimized or avoided with proper contact lens fitting and follow-up. Subjects in the study will be examined within a week after initial contact lens fitting, which is a typical follow-up schedule seen in clinical practice for contact lenses worn in a daily wear modality.

Subject safety will be monitored in the trial through slit lamp evaluation of the ocular surface. Subjects will be educated to potential risk with contact lens wear and instructed to discontinue contact lens wear and contact the study investigators immediately if they experience any eye discomfort, excessive tearing, vision changes, redness of the eye, or other problems

14.0 Potential Benefits to Subjects

14.1 While there are few direct benefits to the study subjects, subjects will be unmasked (told what each of their study lenses were) at the end of the study. Through this they may learn more about their vision and visual performance with different types of contact lenses.

15.0 Provisions to Monitor Data to Ensure the Safety of Subjects

N/A

16.0 Withdrawal of Subjects

FULL PROTOCOL TITLE: Toric Contact Lens Digital Performance and Comfort Study

16.1 Subjects may withdraw consent to participate in the study at any time.

16.2 Subjects may be withdrawn from the trial by the study investigators if they fail to return for study visits or follow study instructions, have unacceptable vision or fit with the contact lenses, are unable to complete the study outcomes, become pregnant during the trial, or have a study-related adverse event that warrants study withdrawal.

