5.0 Number of Subjects

5.1 The proposed single-site study will be conducted at the University of Houston College of Optometry. Up to 30 subjects will be screened for study inclusion, with the goal of completing 24 subjects.

Source data will be collected on paper case report forms and then double entered electronically into a database by trained personnel prior to locking the dataset for analysis.

5.2 In this within-subject crossover design, a paired T-test will be used to compare visual acuity performance, contact lens discomfort, subjective visual quality and LTB4 concentration following toric lens wear to spherical contact lens wear. We will use a two-sided independent T-test to ensure there are no carry over or period effects in our cross-over design, although it is not anticipated. As a secondary outcome, subjects will be asked their preference of contact lenses in a two-alternative forced choice format.

FULL PROTOCOL TITLE: Toric Contact Lens Digital Performance and Comfort Study

One-sample binomial tests will be used to test the hypothesis that the probability of preference to toric lens and spherical lenses are equally likely. Linear mixed model or generalized linear model, as appropriate, will be carried out to examine the associations between eye comfort, visual performance, subjective visual quality and LTB4 concentration during toric and spherical contact lens wear.

We aim to test the hypothesis that $H_0: \Delta=0$ v. $H_1: \Delta \neq 0$ using a two-sided test with significance level $\alpha=0.05$, where Δ is the underlying benefit for treatment contact lenses versus spherical contact lenses in this cross-over design. Our previous work found that toric correction improved visual acuity compared to spherical correction by 6 and 11 letters for high and low contrast logMAR, respectively ($P < 0.001$).¹⁰ To demonstrate an improvement of this amount or more it will require at least 24 and 15 subjects with a $P=0.05$ and 80% power. The dynamic visual acuity test is novel and has not been used previously to allow sample size estimates. A total of 30 subjects will be enrolled to allow for up to 20% dropout/screen-failure/missing data and have 24 subjects complete. We will randomize an equal number of subjects to each group (i.e., group A receives treatment 1 in period 1 and treatment 2 in period 2; group B receives treatment 2 in period 1 and treatment 1 in period 2).

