8.0 Study Timelines

8.1 The total duration of an individual subject's participation in the study will be less than 1 month. The study will consist of 5 visits. Visit 1 will be a baseline evaluation, pre-fitting assessment, randomization, and contact lens fitting. Visits 2 and 4 will be contact lens follow-ups. Visits 3 and 5 are outcome visits and will be performed after 6-8 hours of contact lens wear to provide consistent duration of lens wear between subjects and lens types. The 6-8 hours of wearing time also allows a better understanding of end of day visual performance and the changes in LTB4. Expected visit timing is summarized in the table below:

| |
|---------------------------------------|
| Anticipated Visit Timing and Duration |
|---------------------------------------|

FULL PROTOCOL TITLE: Toric Contact Lens Digital Performance and Comfort Study

| Study Window | Study Visit | Duration |
|--------------|---|---------------|
| Day 1 | Visit 1: Baseline, randomization, contact lens fitting, tear collection | 140 minutes |
| Day 3 ± 1 | Visit 2: Contact lens follow-up | 30-50 minutes |
| Day 10 ± 2 | Visit 3: Outcome lens #1, subjective and objective visual assessments and tear collection, re-fit to lens #2 | 95 minutes |
| Day 13 ± 2 | Visit 4: Contact lens follow-up | 30-50 minutes |
| Day 20 ± 2 | Visit 5: Outcome lens #2, subjective and objective visual assessments and tear collection and tear collection | 75 minutes |

The anticipated duration to enroll and complete all study subjects is approximately 9-12 months. The estimated date for the investigators to complete analyses for this study is Fall/Winter 2021.

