9.2 This is a minimal risk study so safety endpoints are not required

10.0 Procedures Involved

10.1 The study is a clinical trial and will be registered on ClinicalTrials.gov prior to subject enrollment.

10.2 Patients will be seen for 5 visits over a period of approximately 1 month. Visit 1 will determine subject eligibility for the study. Visits 2 and 4 are contact lens follow-up visits. Visits 3 and 5 are study outcome visits. Tests of visual performance at a near reading distance will be evaluated with an iPad application developed by [name]. These applications are designed for research purposes only and are not commercially available. The applications can measure reading speed and provide information on how a subject interacts with the electronic device (e.g. blink rate, working distance from the device, scrolling and zooming on the page, etc.).

10.3 Subjects will be randomized to start with either toric lenses or spherical correction (FDA approved lenses will be utilized).

Overview of Visit Procedures (Assessments)

FULL PROTOCOL TITLE: Toric Contact Lens Digital Performance and Comfort Study

A masked examiner will perform all outcome measures.

| | Visit 1 Baseline and Fit Lens 1 | Visit 2 day 3±1 | Visit 3 – day 10±2 | | Visit 4 day 13±1 | Visit 5 day 20±2 |
|--|--|-------------------------|-----------------------|---------------|-------------------------|---------------------|
| | | Follow- up Lens 1 | Outcomes Lens 1 | Fit Lens 2 | Follow- up Lens 2 | Outcomes Lens 2 |
| Informed consent | X | | | | | |
| Ocular/medical/contact lens history | X | | | | | |
| Ocular symptoms (CLDEQ-8) ⁸ | X | | X | | | X |
| Auto-refraction and keratometry | X | | | | | |
| Slit lamp exam with NaFl staining | X | | | | | |
| Manifest refraction | X | | | | | |
| Accommodation and phoria | X | | | | | |
| Near logMAR HCHL & LCHL acuity OU | X | | X | | | X |
| NAVQ survey ⁵ | X | | X | | | X |
| Radner reading sentences, dynamic acuity measurement and functional vision test with iPad ⁴ | X | | X | | | X |
| Tear collection | X | | X | | | X |
| Study lens order randomization | X | | | | | |
| Insertion of CL and settling (15 min) | X | | | X | | |
| Clinical CL vision and fit assessment, over-refraction, and power adjustment if indicated | X | X | | X | X | |
| Removal of study lens and slit lamp exam with NaFl staining | | X | X | | X | X |

FULL PROTOCOL TITLE: Toric Contact Lens Digital Performance and Comfort Study

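### Does withdrawal for unacceptable vision or fit, with no exit acuity planned, bias the lens comparison enough to change the plan?

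*Protocol*

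**What the plan says.** Near visual acuity is the only primary endpoint (Protocol 9.1). In the visit table under section 10.3, the row "Near logMAR HCHL & LCHL acuity OU" is marked at Visits 1, 3 and 5. The Visit 1 entry stands above randomisation and lens insertion, so I read it as a baseline value. Each study lens then has one scheduled near-acuity outcome.

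The row "Clinical CL vision and fit assessment, over-refraction, and power adjustment if indicated" is marked at Visits 1 and 2 for the first lens, and at the Visit 3 refit and Visit 4 for the second. Section 16.2 permits, but does not require, withdrawal of subjects who "have unacceptable vision or fit with the contact lenses, are unable to complete the study outcomes". Early exit is otherwise mentioned only in connection with payment (section 17.2).

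Outcome visits follow 6-8 hours of wear "to provide consistent duration of lens wear between subjects and lens types" (section 8.1), and "A masked examiner will perform all outcome measures" (section 10.3).

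For analysis, section 5.2 says "a paired T-test will be used to compare visual acuity performance". The SAP instead uses a linear mixed model with sequence and lens as fixed factors. The SAP has no rule for withdrawals or missing outcomes.

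**The concern.** The reason for withdrawal is a judgement about vision, in a trial whose endpoint is vision, and it is made before the endpoint is recorded. If subjects who see badly with one lens leave before that lens's outcome visit, those who remain are a selected group. A paired analysis drops the leavers entirely. A mixed model can keep a completed first period, but the missing value still depends on something unobserved, so the bias remains.

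The direction depends on which lens prompts the exit. Exits for poor vision with the sphere shrink the toric benefit; exits for poor vision with the toric lens inflate it. The 20% allowance in section 5.2 protects the number of completers, not against selective loss. The fitting examiner is not among those described as masked (section 12.1), so the judgement need not be blind to lens.

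**Working it through.** **Inputs from the Protocol (section 5.2).** Benefit of 6 letters (high contrast), two-sided alpha 0.05, 80% power, "it will require at least 24 and 15 subjects" for high and low contrast respectively, and up to 30 enrolled.

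**Plan's own figure.** 24 / (1 − 0.20) = 30, as stated.

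**SD of the paired difference.** It is not given. Solving the noncentral-t power equation for 0.80 at n = 24 gives a standardised effect of 0.597, so SD = 6 / 0.597 = 10.05 letters. The standard error is 10.05/√29 = 1.87 with one loss from 30 and 10.05/√27 = 1.93 with three.

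**Assumptions.** All 30 are randomised (an upper bound, because section 5.1 says up to 30 are screened); one to three exits; within-subject correlation ρ of 0.3, 0.5 or 0.7; correlation r between the clinical judgement and near acuity of 1, 0.5 or 0.

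**Shift when all exits come from one lens.** With equal SDs for the two lenses, the correlation between one lens's acuity and the toric-minus-sphere difference is, in absolute value, c = √((1 − ρ)/2) = 0.592, 0.500, 0.387. Let A be the sum of the k largest expected standard normal order statistics of 30: A = 2.043 for k = 1 and 5.023 for k = 3. Then shift = r × c × 10.05 × A / (30 − k).

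- r = 1, one exit: 0.592 × 10.05 × 2.043 / 29 = 0.42; the other two correlations give 0.35 and 0.27.
- r = 1, three exits: 0.592 × 10.05 × 5.023 / 27 = 1.11; the others give 0.93 and 0.72.
- r = 0.5: half of these, so 0.14-0.21 for one exit and 0.36-0.55 for three.
- r = 0: zero.

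Simulation of the paired t-test (100,000 trials) agrees: three sphere exits at r = 1 leave a mean of 4.89, 5.06 and 5.26 letters. As a fraction of the standard error, the worst case is 0.72/1.93 = 0.4 to 1.11/1.93 = 0.6. Power with three sphere exits is 72-76% at r = 1, 78-80% at r = 0.5 and 85% at r = 0.

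**Low contrast.** The implied SD from n = 15 and 11 letters is 14.14. The same worst case is 0.592 × 14.14 × 5.023 / 27 = 1.56 letters, or 14% of 11, against 1.11/6 = 18% for high contrast.

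**SAP mixed model.** Simulated with completed first periods kept, three exits shift the estimate by 1.0-1.3 letters at r = 1 and 0.5-0.65 at r = 0.5. That is slightly worse than the paired analysis, so the model is no remedy, but the size is similar.

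**One vision cutoff for both lenses.** With toric acuity 6 letters better and r = 1, most exits are on the sphere, and three exits lower the estimate by 0.41-0.71 letters. At r = 0.5 the fall is 0.16-0.34 if the judgement carries the full 6-letter advantage and 0.09-0.17 if it carries half. The net effect is against the toric lens.

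**Exit acuity.** Adding exit values to the mixed model removes the shift if they equal the outcome-visit value. If all are wrong by 5 letters in one direction (assumed), three exits leave an error of 0.3-0.45 letters. That is better than no exit value at r = 1 or 0.5, and worse at r = 0, where there was nothing to correct.

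**The case for a change.** The case for a change is reasonable. The structural facts are as described, a judgement-driven loss cannot be repaired by the model, and the study-lens near acuity of someone who leaves is gone for good. The exit count is my assumption, because the documents give no rate. If the whole allowance of six were lost this way, each with a difference 1 SD from the mean, the retained mean would be (30 × 6 − 6 × 16.05) / 24 = 3.49, a shift of 2.51 letters. Losing exactly the six worst acuities with one lens would cost 1.3-2.0 letters. Starting from 27 randomised, the extreme three-exit case leaves power of 65-70%. The proposed remedy is one chart test already in use.

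What stands is that a small bias is conditional on few exits. The six-exit case needs the entire allowance, which also covers screen failures, ordinary dropout and missing data, to go to vision exits on one lens. That is hard to square with power adjustment at every fitting and follow-up, cylinder limited to -0.75 to -1.50, best corrected acuity of 20/25 or better, and established soft lens wearers.

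The remedy is also less simple than it sounds. At Visit 1 and the Visit 3 refit, acuity would follow about 15 minutes of settling. At Visits 2 and 4 it would have to precede the step listed as "Removal of study lens and slit lamp exam with NaFl staining", at a wear time that the protocol does not state. It would also need a masked examiner at visits where no near-acuity outcome is scheduled. The loss is not wholly uncheckable either: every subject has a baseline near acuity, and each lens has clinical vision checks before its outcome visit.

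**Conclusion.** No change to the plan. The mechanism is real, but no stated rule or figure is wrong and the primary analysis would stay the same. With one to three exits from at most 30 randomised, an implied SD of 10.05 letters and within-subject correlation of 0.3-0.7, the shift is at most about 1.1 letters in the paired analysis and 1.3 in the mixed model. Both figures require exits to be exactly the worst near acuities on a single lens; a looser link gives about half, and exits for fit alone may give none. If one standard is applied to both lenses, the bias runs against the toric claim.

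An exit acuity is a debatable trade: it helps when exits track near acuity, adds error when they do not, and breaks the fixed wear time. The SAP, dated 20 Dec 2021 and written in the past tense, suggests that collection is over in any case. What remains is ordinary reporting of withdrawals by lens, period and reason, which analysts can supply without amending anything. The conclusion would weaken only if that account showed many vision exits concentrated on one lens.

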17.0 Costs/Payments to Subjects

17.1 There are no expected additional costs to subjects that participate in the study. There is no cost to subjects for contact lens fitting in this study.

17.2 Subjects will be provided with daily disposable contact lenses for the duration of the study at no charge. Subjects parking at each study visit will be validated (if necessary). Subjects will be compensated \$50 for completion of each study visit (a total of up to \$250 for 5 visits). Subjects will be compensated with an Amazon gift card after completion of the last study visit or exit from the study (if early exit).

18.0 Compensation for Research-Related Injury

18.1 The risks to subjects from participation in the study are minimal. The clinical procedures used in the study are commonly used clinical procedure in optometry and ophthalmology. In the rare case that a subject is injured as part of their participation in the study, the subject will be responsible for any associated medical bills.

19.0 Confidentiality

19.1 Subjects will be assigned a unique subject ID. Subjects IDs are two digits and should start at 01 and continue in the order of enrollment.

19.2 Any source documents with patient identifiable information will be kept only at the local site (informed consent form, linking log). Individual documents will be kept in a locked room in the [name] lab.

19.3 No one outside of the research team will have access to the subject identifiers.

19.4 A key to the study code will be maintained for 3 years at the time of study completion (i.e. Last Subject, Last Visit).

19.5 No audio or video will be saved in this study. The video recorded during the digital performance testing is only used to verify blinks and test distance/alignment and will be deleted once testing is verified. Only the numerical data will be saved.

20.0 Provisions to Protect the Privacy Interests of Subjects

FULL PROTOCOL TITLE: Toric Contact Lens Digital Performance and Comfort Study

20.1 Those who are potentially eligible and interested in the study will be referred to a study team member who will discuss the study with them. This discussion will take place in a quiet, private area and as much time as necessary will be spent discussing the details of the study.

21.0 Informed Consent Process

21.1 This trial will follow the University of Houston Division of Research SOP: Informed Consent Process for Research (HRP-090). The participant will be provided an opportunity to read the informed consent and to have any questions answered before agreeing to participate. Prior to any testing, the investigator or study coordinator will obtain written informed consent from all participants. The consent form will be signed and dated by both the participant and a member of the study personnel who has been approved to obtain consent. The participant will receive a copy of the signed consent documents and the originals will be filed in the subject binder on site in a secure location.

21.2 Potential individuals who cannot understand English, or who are unable to consent, will not be included in this study.

22.0 Process to Document Consent in Writing

22.1 The clinical trial will follow the University of Houston Division of Research standard operating procedure regarding written documentation of informed consent (SOP: Written Documentation of Consent (HRP-091)). The consent form will be signed and dated by both the participant and a member of the study personnel who has been approved to obtain consent. The participant will receive a copy of the signed consent documents and the originals will be filed in the subject binder on site in a secure location.

22.2 Template Consent Document HRP-502c will be used for consented adults

22.3 A copy of the informed consent document is included in the study related documents.

23.0 HIPAA

23.1 We will be collecting demographic information and general medical and eye health information. Since protected health information (PHI) will be collected, the Health Insurance Portability and Accountability Act (HIPAA) authorization form will be included as part of the Informed Consent process.

23.2 The link to PHI will be destroyed upon completion of the study and final analysis/report. PHI will not be reused or disclosed to any other person or entity, except as required by law, for authorized oversight of the research study, or for other research for which the use or disclosure of protected health information for which an authorization or opportunity to agree or object is not required by 45 CFR 164.512.

24.0 FERPA

N/A

25.0 Data Management

25.1 Any source documents with patient identifiable information will be kept only at the local site (informed consent form, linking log). Individual documents will be kept in a locked room in the [name] lab. Paper source documents (i.e. case report forms) will only be associated with a subject ID number and will not contain direct subject identifiers. Data will be entered in Excel for analysis and no patient identifiers will be entered in the data analysis spreadsheets.

25.2 Data Entry will be conducted by study team members and data will be doubled checked for any errors.

25.3 Electronic data will only be stored in a limited access shared folder on the college directory.

25.4 Copy of the data will be stored on campus for 3 years following completion of the research.

25.5 Only study team members will have access to the study data.

25.6 Data can only be accessed remotely via the secure UH VPN system.

